### **3.4 Identification of participants and consent**

Patients will be identified by the CI or other clinician responsible for the patient. Patients will be screened at this time to establish eligibility. The inclusion/exclusion criteria will be evident from the information taken as part of the normal clinical procedure (eg history, examination and treatment plan). Eligible patients will be initially informed of the existence of the study and approached by the consultant or his/her representative who is treating the patient (E.g. specialist trainee/house officer/GDP/DCP). This initial contact will be to provide the patient with the Participant Information Leaflet (PIL) and establish whether they would consider taking part. At the subsequent visit, (Screening visit), the CI/CO/Registrar/consultant or research nurse will ask whether the patient would like to take part and obtain consent. At each stage, it will be made clear to the patient that that participation is voluntary and they can leave the study at any time without their care being affected.

### **3.5 Withdrawal of subjects**

Patients will be withdrawn for the study if they are no longer eligible (e.g. due to a change in general health) or if the patient withdraws their consent to participate, or if for any other reason the CI or patient's consultant deems it detrimental to the patient to continue to participate. Withdrawal will be immediate. The CI will be informed and will confirm whether the patient wishes any previously obtained samples and associated data withdrawn from the study. The reason for withdrawal and the subsequent action taken will be documented on a case-by-case basis as an addition to the case report form (CRF).

## **4 Trial procedures**

### **4.1 Study schedule**

Patients will attend Glasgow Dental Hospital for screening, baseline, treatment, then Day 1 after treatment, Day 7 after treatment, and review (day 90 after treatment). Screening visits may be undertaken by GDP. The visits are labelled as per the flow chart/table with the purpose of the visit.

#### **Screening visit: New patient assessment**

Patients are referred then appointed on a new patient consultant clinic at which a clinical history and clinical examination are completed by the consultant or his/her staff. A treatment plan is then agreed with the patient. If this treatment plan includes periodontal treatment at Glasgow Dental Hospital and the patient is eligible to take part, then the patient will be provided with written and verbal information about the study. The patient will be asked to give an initial indication as to whether they would consider taking part – with emphasis that they should take time to consider the PIL and will have the opportunity to ask further questions, and that their treatment remains unaltered irrespective of their participation. If the patient indicates they would consider participation in the study, they will be appointed jointly to the GDHCRF and the hygienist / registrar (baseline visit).

#### **Baseline visit:**

If the patients initially said YES to participating in the study at the screening visit, at this visit, prior to the start of treatment the patient will be asked if they have further considered participation in the study. If yes, consent for sample collection will be sought and samples will be collected by the GDHCRF research nurse and/or dentist/hygienist (the hygienist or dentist will generally only collect plaque samples as s/he will be removing the plaque anyway). This visit includes FMPS & FMBS & Periodontal charting, blood pressure recording, BMI recording and sample collection of GCF, plaque & blood). This visit is also for initial periodontal charting and initial treatment. This visit includes detailed tooth and gum home care instructions and a superficial scaling of the teeth. This is usually carried out by a staff or research hygienist, but may also be undertaken by training grade staff under the supervision of a consultant.

gingival indices will be taken. The patient will then be randomised to full mouth non-surgical periodontal treatment using either hand scalers or ultrasonic instrumentation. Appointments will be made for patient to attend for treatment visits, Day1, Day 7 and Day 90 visits with time in the GDHCRF for sample collection / blood pressure, BMI and periodontal charting where applicable.

**Treatment visits** - full mouth non-surgical periodontal treatment will be carried out within a 24hr period (+/- 18hr) either using hand instrumentation or ultrasonic instrumentation as per randomization. At the last treatment visit the clinician will verbally enquire whether the patient is happy to continue participation in the study. If yes - then the patient should attend Day 1 (24hrs later (+/- 18hrs) with time in the GDHCRF for sample collection / blood pressure recording.

**Day 1** - 24 hours (+/-18hrs) after treatment completed, further samples (GCF/Plaque/blood) and blood pressure recording will be performed. At this visit the clinician will verbally enquire whether the patient is happy to continue participation in the study. If yes - then the patient should attend Day 7 (+/- 1 day) with time in the GDHCRF for sample collection / blood pressure recording, & review of ohi

**Day 7** – 7 days after treatment completed, further samples (GCF/Plaque/blood) and tests (blood pressure recording and medical history update) will be performed. At the last treatment visit the hygienist will verbally enquire whether the patient is happy to continue participation in the study. If yes - then the patient should attend the Day 90 visit (+/- 10days) with time in the GDHCRF for sample collection / blood pressure recording, plaque index & review of oral hygiene.

**Day 90** - 90 days after treatment (+/- 10 days) Patient appointed jointly to the GDHCRF and for review with consultant or training grade staff / hygienist under consultant supervision. FMPS & FMBS & periodontal charting, medical history, blood pressure recording, BMI & sample collection of GCF/ Plaque / blood will be taken as at baseline, day 1 and day 7 visits.

## 4.2 Study Outcome Measures

### 4.2.1 Primary Outcome Measure

*Changes in serum CRP pre compared with post treatment.*

### 4.2.2 Secondary Outcome Measure

To investigate: **Secondary Outcomes:**

Microbiome (continuous and discrete data)

- Microbiome analysis of plaque
- Species diversity
- Collected pre intervention (at baseline visit)
- Collected post intervention (at day 1)

Bacteraemia analysis (continuous data)

- Collected simultaneously with serum CRP
  - Day 1, day 7 and day 90 post intervention

Inflammation and immune analysis (continuous data)

- GCF – cytokine measurements
- Serum cytokine measurement
- Serum antibody (anti-bacterial/auto antibody)
- Collected simultaneously with serum CRP
  - Day 1, day 7 and day 90 post intervention

Clinical outcomes (discrete data)

- Periodontal Probing Depths (at day 90 post intervention)
- Loss of attachment (at day 90 post intervention)
- Plaque/gingival indexes
- Blood pressure recording
- Treatment time (time spent on debridement)

Patient centered outcomes (Questionnaire data - qualitative/quantitative)

- Patient satisfaction and experience

Clinician centered outcomes – (Interview data - qualitative/quantitative)

- Experience with each instrumentation technique

## 4.3 Laboratory Tests

The laboratory analysis will be carried out in University research labs using appropriate methodology. The laboratory research group has significant experience in these techniques and works within a large group of research scientists within the University of Glasgow Dental School and Institute for Infection, Immunity and Inflammation – thereby granting access to substantial expertise.

## **5. STATISTICS AND DATA ANALYSIS**

### **5.1 Statistical analysis plan**

Randomized controlled trial to investigate the difference in systemic response to periodontal therapy, using two different treatment modalities – hand instrumentation and ultrasonic instrumentation. Patients will receive one of two interventions – hand instrumentation or ultrasonic instrumentation, as treatment for their periodontal disease. These two interventions will be compared through the following outcomes.

The primary outcome is that of systemic inflammatory response, measured through serum CRP. A variety of secondary outcomes will also be investigated, including clinical outcomes related to periodontal disease; microbiome analysis; inflammation and immune response analysis.

#### ***Stratification and Randomization Methods***

Our target population is that of patients suffering from periodontal disease.

Randomization to either intervention (hand instrumentation or ultrasonic instrumentation) will be performed using a computerised random number generator (using permuted blocks of size 4 and 6). Patients will be stratified according to smoking status prior to randomization.

#### ***Allocation Concealment***

Patients will be allocated to each arm of the study by a member of the research team not involved with the clinical delivery of the experimental interventions. Upon attending their treatment appointment, an opaque envelope will contain the allocated intervention arm for the patient. This will be opened immediately before treatment is commenced.

#### ***Blinding***

Both the patients and clinicians will remain blinded to the intervention until the intervention is carried out. Research personnel will remain blinded to specific patient allocation throughout the process through the means of patient barcodes. The key linking the barcodes to the patients will be available to the Chief Investigator. The intervention codes will only be available once the key analyses have taken place.

#### ***Sample Size***

The sample size calculation is based on data from previous published studies that measured changes in CRP following periodontal treatment. From these studies a difference of 3.5 mg/l (SD=3 mg/l) in CRP was detected between the two groups receiving different schedules of periodontal treatment (quadrant vs full mouth debridement) at primary endpoint. Therefore at 80% power and a 5% significance level, a sample size of n=34 (17 in each group) is required to detect a minimum difference of at least 1 standard deviation (3 mg/l) between the change in CRP levels from baseline to primary endpoint between the two groups (hand vs ultrasonic). To account for potential drop out of 20% we aim to recruit 42 eligible patients to the study.

#### ***Study Population***

The study will aim to recruit a minimum of 17 patients per group, up to 21 patients per group (to account for drop out) requiring periodontal treatment within a

recruitment period of 18 – 24 Months. The patients will be recruited from new patient clinics in the periodontal department of Glasgow Dental Hospital, Scotland

### **Statistical Analysis Plan (SAP)**

#### **Objectives**

To determine if there is a difference in the systemic response to periodontal treatment using either hand instruments, compared to ultrasonic instrumentation.

#### **General Principals**

Data will be summarised for patients in both groups. Categorical variables will be summarised with the number of observations and missing values, and number and percentages of patients falling into each category. Continuous variables will be summarised using the number of observations and number missing, mean, standard deviation (SD), median, 25th and 75th quartiles (Q1 and Q3 respectively), minimum and maximum values. Formal comparisons will be made between the treatment groups using appropriate tests depending on the nature of the data, this may include Chi-Squared tests, Fisher Exact Tests, two sample t-tests and Mann Whitney tests.

Analysis: the effect of treatment group (Manual vs ultrasonic) on changes in CRP levels (and other secondary outcomes):

- Appropriate generalised linear models
- Binary logistic models (for dichotomous outcomes)

Models may be adjusted for age, gender, deprivation levels, operator, smoking, baseline disease levels.

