### 1. INTRODUCTION

#### 1.1 Background

Effective root surface debridement (RSD) is essential for successful periodontal treatment. Myriad studies demonstrate that RSD may be carried out using hand or ultrasonic instruments with equal efficacy (1). Locally, effective debridement results in reduced inflammation in the gingival tissues, ultimately preserving the dentition. Systemically, RSD results in an immediate inflammatory response with elevated C-reactive protein (CRP), and cytokines (e.g. interleukin-6 and Tumor Necrosis Factor) detectable in the serum (2). This systemic inflammation may relate to systemic dissemination of bacteria from the periodontal pockets into the circulation, during instrumentation. Bacteria are detectable in serum immediately after instrumentation (3). The incidence of the bacteraemia varies considerably between different studies,

ranging from 13% of patients (4) to 43% (5) to 55% (6). These studies used different methods of instrumentation; Kinane et al used full mouth ultrasonic scale, Zhang et al used a mixture of hand and ultrasonic instruments, and Heimdahl et al used curettes only. Whilst tempting to speculate that ultrasonic instrumentation induces less bacteraemia than hand instrumentation, *there is no direct comparison of the effect of ultrasonic instrumentation with hand instrumentation on post treatment systemic inflammation.*

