#### **Primary Outcome:**

Changes in serum CRP. This will be measured:

- Pre-intervention, at baseline visit (as per flowchart)
- Day 1, day 7 and day 90 post-intervention

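### Baseline CRP is not a required covariate in the analysis of change in CRP, so the plan permits an unadjusted change-score comparison that is usually less precise

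*Combined protocol and SAP*

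**What the plan says.** Section 4.2.1 defines the primary outcome as "Changes in serum CRP pre compared with post treatment". The SAP (section 5.1, Primary Outcome) has CRP measured at the baseline visit and then at "Day 1, day 7 and day 90 post-intervention", so each patient should have a pre-treatment value.

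The analysis is described only in the SAP under General Principals. Its target is "the effect of treatment group (Manual vs ultrasonic) on changes in CRP levels (and other secondary outcomes)", to be estimated with generalised linear models that are not specified further. Group comparisons may also use two-sample t-tests or Mann-Whitney tests. On covariates it says: "Models may be adjusted for age, gender, deprivation levels, operator, smoking, baseline disease levels". No covariate is compulsory, and baseline CRP is not on the list. Section 5.2, where a primary analysis would be expected, says there is none because there is no test intervention.

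The Sample Size text takes its inputs from published work: "From these studies a difference of 3.5 mg/l (SD=3 mg/l) in CRP was detected between the two groups receiving different schedules of periodontal treatment". It then sizes the trial at 17 per group for a "difference of at least 1 standard deviation (3 mg/l) between the change in CRP levels from baseline to primary endpoint".

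**The concern.** When the outcome has a baseline measurement, there are two common ways to compare the arms: compare mean changes directly, or regress the endpoint (or the change) on treatment with the baseline value as a covariate. In a randomised trial both estimate the same difference. The second uses the information in the baseline more efficiently, apart from one degree of freedom. This plan leaves the choice open and does not name the covariate most directly tied to the outcome.

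Two things are at stake. The first is precision: the trial is small and is sized to just over 80% power, so an inefficient analysis matters more than it would in a large trial. The second is discretion: because adjustment is optional, the primary model can be settled after the data have been seen.

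**Working it through.** **Inputs from the Sample Size text:** difference 3 mg/l, SD 3 mg/l, 17 per arm, 5% significance, 80% power. Two-sided testing is assumed because the hypothesis in section 1.4 has no direction.

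**Inputs the documents do not give (assumed, shown as a range):** r, the correlation between baseline and endpoint CRP; and k = baseline SD / endpoint SD.

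**The plan's own figure.** A two-sample t-test with a standardised difference of 3/3 = 1 needs 16.71, so 17, per arm (34 in total), and its power at 17 per arm is 80.7%. The stated 34 is therefore reproduced by an unadjusted comparison of changes with SD 3 mg/l.

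**Formulas.** With S the endpoint SD:

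- variance of the change = S²(1 + k² − 2rk)
- residual variance after adjusting for baseline = S²(1 − r²)
- difference between the two = S²(k − r)²

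The adjusted variance is never larger, and the two are equal only when r = k. Power is from the noncentral t distribution with noncentrality (3/SD)·√(17/2), on 32 df (change score) or 31 df (adjusted).

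**Reading A: 3 mg/l is the SD of the change.** Then S = 3/√(1 + k² − 2rk), and unadjusted power is 80.7% throughout. Example, k = 1 and r = 0.5: S = 3/√1 = 3, and adjusted SD = 3·√0.75 = 2.60.

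| k | r | Adjusted SD | Unadjusted power | Adjusted power |
|---|---|---|---|---|
| 1 | 0.3 | 2.42 | 80.7% | 93.8% |
| 1 | 0.5 | 2.60 | 80.7% | 90.3% |
| 1 | 0.7 | 2.77 | 80.7% | 86.5% |
| 0.5 | 0.3 | 2.94 | 80.7% | 82.3% |
| 0.5 | 0.5 | 3.00 | 80.7% | 80.6% |
| 0.5 | 0.7 | 2.89 | 80.7% | 83.5% |

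**Reading B: 3 mg/l is the SD of CRP at the endpoint (S = 3).** Change SD = 3·√(1 + k² − 2rk); adjusted SD = 3·√(1 − r²).

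| k | r | Change SD | Adjusted SD | Unadjusted power | Adjusted power | Per arm for 80%: unadjusted v adjusted |
|---|---|---|---|---|---|---|
| 1 | 0 | 4.24 | 3.00 | 51.6% | 80.6% | 33 v 17 |
| 1 | 0.3 | 3.55 | 2.86 | 66.6% | 84.1% | 23 v 16 |
| 1 | 0.5 | 3.00 | 2.60 | 80.7% | 90.3% | 17 v 13 |
| 0.5 | 0 | 3.35 | 3.00 | 71.5% | 80.6% | 21 v 17 |
| 0.5 | 0.3 | 2.92 | 2.86 | 82.6% | 84.1% | 16 v 16 |
| 0.5 | 0.5 | 2.60 | 2.60 | 90.4% | 90.3% | 13 v 13 |

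**Check by simulation** (40,000 trials per setting, random baseline values). Adjusted power came out up to about 1.5 points below the formulas: under reading B with k = 1 it was 79.6%, 82.6% and 89.3% at r = 0, 0.3 and 0.5. At k = r = 0.5, where the change score is optimal, unadjusted v adjusted power was 80.6% v 79.4% (reading A) and 90.2% v 89.2% (reading B). The mean estimate was 3.0 mg/l for both methods, so neither is biased.

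**The case against.** The strongest reply is that the benefit is unknown rather than shown. The largest gaps (51.6% v 80.6%; 33 v 17 per arm) need reading B, equal SDs and zero correlation all at once. Section 1.1 expects treatment to raise CRP ("Systemically, RSD results in an immediate inflammatory response with elevated C-reactive protein (CRP)"), so a baseline SD well below the endpoint SD is plausible. That is where the gain can shrink to a few points or vanish. Reading A also fits the text better, because it reproduces 17 per arm, and on that reading the unadjusted test delivers the power the trial was designed for. All of this stands, and it is why the size is given as a range.

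Other points reduce the weight without removing the concern:

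- **Margin.** The source difference was 3.5 mg/l, at which 17 per arm gives 91.0% power. With no dropout, 21 per arm gives 88.5% for 3 mg/l. Neither cushion is assured: the target difference is 3 mg/l, and at the assumed 20% dropout 42 × 0.8 = 33.6 patients remain.
- **Masking.** The protocol masks the person doing the analysis and withholds the intervention codes until the key analyses are done. That limits steering, but a model can still be chosen after looking at results by coded arm.
- **Permission.** The plan does not forbid adjusting for baseline CRP, and its undefined term for baseline disease could be stretched to cover it. The synopsis lists clinical measures of periodontal severity separately from serum CRP, so severity is the more natural meaning. On either reading the adjustment stays optional.
- **Distribution.** All the power figures assume normal data, while the SAP also allows rank tests.

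**Conclusion.** The concern holds and should be fixed. The plan collects baseline CRP but does not require its use as a covariate, and nothing elsewhere in the documents fixes the primary model. The defect is one of precision and analyst discretion. The change-score estimate is unbiased, and the sample size is correct on its own inputs if 3 mg/l is the SD of the change.

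On that reading, adjustment adds about 6 to 13 points of power at r = 0.3 to 0.7 with equal SDs, and at most about 3 points when the baseline SD is half the endpoint SD. If 3 mg/l is the endpoint SD, the gain over r = 0 to 0.5 runs from nil to 29 points (80.6 − 51.6). The exact gain cannot be stated because r and k are assumptions. The trade-off is nevertheless lopsided: a worst cost of about one point against a possibly substantial gain.

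**What to change.** In the SAP under General Principals, replace the optional adjustment with one fixed primary model, for example:

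> The primary model is a linear regression of CRP at the primary time point (or, equivalently for the treatment effect, of its change from baseline) on treatment group, with baseline CRP as a covariate.

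Apply the same rule to each continuous secondary outcome that has a baseline value. Smoking, the stratification factor, is also only optional at present and can be made a fixed term in the same sentence. If CRP is to be transformed, say so in advance and transform the baseline value in the same way.

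The model can run only once the primary time point is named: the SAP lists three follow-up days, and the Sample Size text does not say which it means. That text should also state whether 3 mg/l is the SD of the change or of CRP at the endpoint and, if the latter, the assumed correlation and baseline SD.

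The cost is two or three sentences of SAP wording and one degree of freedom for baseline CRP (one more if smoking is added as a two-level term). The data are already being collected, and no extra patients are needed.

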#### **3.3 Exclusion criteria**

- Known or suspected high risk for tuberculosis, hepatitis B or HIV infections
- Require interpreter/non English language written material to understand and provide, or any other reason for being unable to provide written, informed consent
- History of bleeding diathesis
- Pregnant or lactating females.
- Reported diagnosis of any systemic illnesses including cardiovascular, renal, and liver diseases, and/or regular use of medication to control systemic illness.
- Any pharmacological treatment within 1 month before the beginning of the study, including routine use of any over the counter medications.
- Specialist Periodontal treatment in the previous 6 months.

Randomisation: patients will be stratified according to smoking status then randomized to one of two groups (hand vs ultrasonic) according to the randomization schedule (permuted blocks of size 4 and 6). The randomization schedule will be computer generated and allocation will be concealed up until the point of treatment. Masking: it will not be possible to mask the clinicians providing the treatment; however the researcher collecting the samples and undertaking the analysis will be masked to group allocation, through the use of anonymised coded samples. All other study personnel will not have access to identifiable data.

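### Smoking is the only stratification factor but only an optional covariate, so the primary CRP analysis may ignore it and give up some power (efficiency, not validity; minor)

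*Combined protocol and SAP*

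**What the plan says.** The design names one stratification factor. The randomisation paragraph under section 3.3 says that "patients will be stratified according to smoking status then randomized to one of two groups". Section 5.1, Stratification and Randomization Methods, repeats it: "Patients will be stratified according to smoking status prior to randomization", with allocation "using permuted blocks of size 4 and 6".

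The analysis text does not carry the factor through. Under General Principals, the SAP offers "Appropriate generalised linear models" for change in CRP and for the secondary outcomes, and then states "Models may be adjusted for age, gender, deprivation levels, operator, smoking, baseline disease levels". For formal comparisons between groups it adds that "this may include Chi-Squared tests, Fisher Exact Tests, two sample t-tests and Mann Whitney tests". Section 5.2, where a primary model could have been fixed, says that there is no efficacy analysis. Nothing elsewhere commits the primary analysis to the smoking stratum.

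The sample size paragraph plans for "a minimum difference of at least 1 standard deviation (3 mg/l) between the change in CRP levels from baseline to primary endpoint". It mentions no strata and no covariates.

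**The concern.** Blocking within smoking strata keeps the arms balanced on smoking, so differences between smokers and non-smokers add little to the true variability of the treatment contrast. An analysis without smoking still counts that variation in its residual. If smoking predicts the change in CRP, the estimated standard error is then too large for the design actually used: type I error falls below 5% and power is lower than it could be.

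At stake is precision in a small trial. With 34 evaluable patients and power just above 80%, a few points matter, and the information needed to recover them is already held at randomisation.

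**Working it through.** **Inputs from the documents.** Difference 3 mg/l, SD 3 mg/l, 80% power, 5% significance, 17 per group (34), 20% dropout, 42 recruited; permuted blocks of 4 and 6 within smoking strata. The significance level is taken as two-sided, because a one-sided 5% test would need only about 14 per group.

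**Assumed, because the documents do not say.** Share of smokers *p* (35%, range 20-50%); difference *g* between smokers and non-smokers in CRP change (0, 1.5 or 3 mg/l); two smoking levels; normally distributed change.

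**Step 1: the plan's own figure.** With a standardised difference of 3/3 = 1, the normal approximation gives 2 × (1.960 + 0.842)² = 15.7, so 16 per group. The noncentral t gives 16.7, so 17 per group with power 80.7%. This reproduces n = 34. For dropout, 34/0.8 = 42.5, and 42 × 0.8 = 33.6, so 42 is within one patient.

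**Step 2: cost of the covariate if smoking is irrelevant.** At 17 per group, power is 80.70% with 32 degrees of freedom and 80.62% with 31, a cost of about 0.1 point. By simulation the cost is 0.1-0.3 points.

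**Step 3: share of variance explained.** With overall SD 3, R² = g²p(1−p)/9. At p = 0.35, g = 1.5 gives 2.25 × 0.2275/9 = 0.057, and g = 3 gives 9 × 0.2275/9 = 0.2275.

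**Step 4: approximation with perfect balance on smoking.** The noncentrality is 3/(3√(1−R²) × √(2/17)). The adjusted test uses the usual critical value on 31 df. The unadjusted test in effect uses its critical value on 32 df divided by √(1−R²). At R² = 0.20, adjusted power is 88.4% and unadjusted power 83.2%. The large-sample type I error of the unadjusted test is 2 × Φ(−1.96/√0.80) = 2.8%.

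**Step 5: simulation.** 20,000 trials per cell, N = 34, blocks of 4 and 6 within strata, 35% smokers, overall SD 3. The two-sample t-test is compared with a linear model in treatment and smoking. Monte Carlo standard error is about 0.15 points for type I error and 0.3 points for power.

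| g (mg/l) | R² | Type I, unadjusted / adjusted | Power, unadjusted / adjusted | Power forgone |
|---|---|---|---|---|
| 0 | 0 | 4.9% / 4.7% | 80.8% / 80.6% | nil |
| 1.5 | 0.057 | 4.5% / 5.1% | 81.1% / 82.4% | 1.3 points |
| 3 | 0.23 | 2.9% / 5.2% | 83.3% / 89.6% | 6.3 points |

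At g = 1.5 and 3 mg/l, the gap is 0.9 and 4.3 points with 20% smokers, and 1.7 and 6.5 points with 50% smokers.

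**Step 6: the other reading of the SD.** If 3 mg/l is the SD within smoking strata, power at 35% smokers and g = 0 / 1.5 / 3 is 80.9 / 79.2 / 74.1% unadjusted and 80.6 / 80.7 / 80.6% adjusted. At 50% smokers and g = 3 the gap is 7.2 points, the largest found.

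**Step 7: dropout.** With 42 randomised, 20% random dropout, 30% smokers, overall SD 3 and R² = 0.20 (8,000 trials), type I error is 3.6% unadjusted and 5.2% adjusted, and power 80.9% and 87.1%. The pattern is unchanged.

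**The case against.** The strongest reply is that the loss may be nil. Every non-zero figure needs a smoking effect that the documents do not give. At 1.5 mg/l, half the difference the trial is sized to detect, the gain is only 1-2 points. The 4-7 point figures need smokers to differ by as much as the planned treatment difference, and nothing in the documents supports that. This stands, and it is why the point is minor.

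A reader might infer that leaving out the stratification factor invalidates the test. It does not: in a linear analysis of CRP change the error is conservative, and no scenario pushed the unadjusted type I error above 5%.

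A reader might also infer that the trial is underpowered without smoking in the model. The 74.1% figure needs both the within-stratum reading of the SD and the largest assumed effect. The sample size paragraph takes its SD from published two-group comparisons and refers to no strata. The within-stratum reading cannot be excluded, but the text does not suggest it. On the overall reading, unadjusted power stays at 80% or above.

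Finally, the same sentence leaves the whole covariate set open. That is a separate and more serious matter: taking the smallest p-value over all 64 subsets of six irrelevant covariates gave a type I error of about 11% in simulation (1,500 runs). Switching only between the unadjusted and the smoking-adjusted model kept it at about 5%. The present point does not rest on this, although the fix also closes the set for the primary model.

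**Conclusion.** The point holds as a minor efficiency issue. The design stratifies by smoking, and the SAP allows a primary analysis that ignores it. If smoking predicts CRP change, that analysis is conservative; if smoking does not predict it, nothing is lost either way. For 34 patients and 20-50% smokers, the power forgone is about 0, 1-2 or 4-7 points for a smoking effect of 0, 1.5 or 3 mg/l, the last being an upper scenario. With SD 3 mg/l as the overall SD, the planned power is kept.

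The direction is firm for a linear analysis; the size is wholly assumed. The figures assume normally distributed change. They do not carry over directly to Mann-Whitney tests or other generalised linear models. Nor do they carry over to the logistic models, where adjusted and unadjusted odds ratios are different quantities.

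**What to change.** Keep the covariate sentence in General Principals for secondary outcomes and sensitivity analyses, and insert before it:

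> *The primary analysis of change in CRP at the primary time point will be a linear model with treatment group and the smoking stratum used at randomisation. Any further covariate in the primary model will be named in the SAP before outcome data by group are seen. Unadjusted tests and models with other covariates from the list below are sensitivity analyses.*

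Two details must be filled in for this to be usable. The SAP must name the primary time point, since it lists days 1, 7 and 90 and the sample size paragraph does not say which is primary. It must also define the smoking categories. With about 34 patients, sensitivity models should stay small and not take all six covariates at once.

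The cost is three sentences and, if smoking has two levels, one degree of freedom (about 0.1-0.3 power points if smoking is irrelevant). Smoking status is already needed to randomise, so there are no new data to collect, and 34/42 is unchanged.
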